## 5 EFFICACY ENDPOINTS

### 5.1 Primary Efficacy Endpoint

The primary efficacy composite endpoint is defined as the geometric mean of the ratios of the maximum PreOp value (Visit 1b or Day 1 PreOp) over Baseline (Visit 1a) for the 3 preconditioning biomarkers,

$$Exp \left\{ \frac{1}{3} \cdot \left[ Log \left( \frac{\text{max PreOp HO-1}}{\text{Baseline HO-1}} \right) + Log \left( \frac{\text{max PreOp Ferritin}}{\text{Baseline Ferritin}} \right) + Log \left( \frac{\text{max PreOp IL-10}}{\text{Baseline IL-10}} \right) \right] \right\}.$$

For sensitivity analysis, this composite endpoint will also be defined as the geometric mean of the ratios of average of Day 1 PostOp through Day 3 over baseline for the 3 preconditioning biomarkers {HO-1, Ferritin, and IL-10}, where Avg (average) is calculated as the area under the biomarker-time curve (AUC) divided by the duration in the AUC calculation (AUC/D), and

$$AUC = \left\{ \sum_{i=2}^n (v_i + v_{(i-1)}) (t_i - t_{(i-1)}) \right\} / 2,$$

$$D = t_n - t_1$$

$v_1$  and  $v_n$  are the first (Visit 1b or Day 1 for subjects dosed 36 to 48 hours or 24 to <36 hours prior to surgery, respectively) and last (Study Day 3) biomarker values after study drug administration,  $t_i$  is the date and time of the  $i^{\text{th}}$  biomarker test.

Baseline for this composite endpoint is calculated as

$$(\text{Baseline HO-1} * \text{Baseline ferritin} * \text{Baseline IL-10})^{1/3}.$$

Because an increase in plasma biomarkers is beneficial and because the ratios are calculated as the follow-up value over the baseline value, a value >1 for the primary efficacy endpoint would indicate benefit.

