## **7.4 Study Subjects**

### **7.4.1 Subject Disposition and Analysis Population**

Number of screened subjects, randomized subjects, study drug-treated subjects, and subjects receiving surgery will be provided overall and by treatment group. In addition, the number of randomized subjects completing the study and the reasons for discontinuation will be summarized overall and by treatment group.

Information on subject disposition will also be listed.

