## 7.5 Efficacy Analysis

Primary endpoint will be analysed using both the ITT and MITT populations. All other efficacy endpoints will be analyzed using the MITT population.

Surgery type and time on pump may be used as covariates in ANCOVA or MMRM, or as stratification factor in Cochran-Mantel-Haenszel (CMH)  $\chi^2$  test. When used as stratification factor, time on pump will be trichotomized by the approximate tertile ( $\leq 90$ ,  $>90$  to  $120$ ,  $>120$  minutes) of the distribution in the MITT population. Other variables (eg, AKI risk factor and investigator site) may also be considered as covariates or stratification factors. The decision for including/excluding these variables as covariates or stratification factors will be based on the blinded review prior to any unblinded analysis.

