### 7.5.1 Primary Efficacy Endpoint Analysis

The primary efficacy endpoint (geometric mean of the ratios of maximum PreOp over baseline in preconditioning biomarkers, Section 5.1) will be summarized using descriptive statistics (N, mean, median, standard deviation, minimum, and maximum) in the log scale and presented after the anti-log (exponential) transformation for each group separately.

An analysis of covariance (ANCOVA) model will be applied to the log-transformed primary efficacy endpoint. The model will include treatment group as main effect, and surgery type and time on-pump as covariates. Least squares mean (LSM) and the 95% confidence interval (CI) will be calculated for each treatment group and for the between active treatment and placebo difference. The LSM (95% CI) will be anti-log transformed and presented as the geometric LSM (GLSM) and 95% CI for each treatment group, and GLSM ratio (and 95% CIs) for each active treatment over placebo.

A sensitivity analysis will be carried out by the Cochran-Mantel-Haenszel (CMH)  $\chi^2$  test for the row mean score difference between active treatment and placebo stratified by the surgery type and time on pump. A modified ridit score will be used in the calculation of the CMH test statistic. As a supplementary analysis for the primary endpoint, each component of the composite endpoint

- $\frac{\text{max PreOp HO-1}}{\text{Baseline HO-1}}$
- $\frac{\text{max PreOp ferritin}}{\text{Baseline ferritin}}$
- $\frac{\text{max PreOp IL-10}}{\text{Baseline IL-10}}$

will be analyzed in the same way as for the primary efficacy endpoint.

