#### Efficacy Endpoints

Table 14.2-1.1.1 Analysis of Primary Efficacy Endpoint (Geometric Mean of the Ratios of Max PreOp over Baseline in Preconditioning Biomarkers) - ITT Population

Table 14.2-1.1.2 Analysis of Primary Efficacy Endpoint (Geometric Mean of the Ratios of Max PreOp over Baseline in Preconditioning Biomarkers) - MITT Population

Table 14.2-1.1.3 Analysis of Primary Efficacy Endpoint (Geometric Mean of the Ratios of Average PostOp over Baseline in Preconditioning Biomarkers) - MITT Population

Table 14.2-1.2.1 Analysis of the HO-1 Component of the Primary Efficacy Endpoint (Ratio of Max PreOp over Baseline) - MITT Population

Table 14.2-1.2.2 Analysis of the Ferritin Component of the Primary Efficacy Endpoint (Ratio of Max PreOp over Baseline) - MITT Population

Table 14.2-1.2.3 Analysis of the IL-10 Component of the Primary Efficacy Endpoint (Ratio of Max PreOp over Baseline) - MITT Population

Table 14.2-2.1.1 Analysis of Secondary Efficacy Endpoint (Geometric Mean of the Ratios of Max PostOp over Baseline in Tubular Injury Biomarkers) - MITT Population

Table 14.2-2.1.2 Analysis of Secondary Efficacy Endpoint (Max of Max PostOps over Baseline in Tubular Injury Biomarkers) - MITT Population

Table 14.2-2.2.1 Analysis of the Ratio of Max PostOp over Baseline in KIM-1 - MITT Population

Table 14.2-2.2.2 Analysis of the Ratio of Max PostOp over Baseline in Cystatin-C - MITT Population

Table 14.2-2.2.3 Analysis of the Ratio of Max PostOp over Baseline in NGAL - MITT Population

Table 14.2-3.2 Subject Incidence of Sustained Urine Reduction Reported as an AE - MITT Population

Table 14.2-4.2 Subject Incidence of Revised Acute Kidney Injury (AKI) - MITT Population

Table 14.2-5.1 Analysis of Mean Change and Percent Mean Change from Baseline to PostOp Through Day 7 (or Early Discharge) in Serum Creatinine (mg/dL) - MITT Population

Table 14.2-5.2 Analysis of Change and Percent Change from Baseline to Each PostOp Visit in Serum Creatinine (mg/dL) MITT Population

Table 14.2-6.1 Analysis of Mean Change and Percent Mean Change from Baseline to PostOp Through Day 7 (or Early Discharge) in eGFR (mL/min/1.73m^2) - MITT Population

Table 14.2-6.2 Analysis of Change and Percent Change from Baseline at Each Visit in eGFR (mL/min/1.73m^2) - MITT Population

Table 14.2-7.1 Subject Incidence of Major Adverse Kidney Events (MAKE) Post Surgery - MITT Population

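### SAP 7.5.1 adjusts and stratifies the pre-operative primary endpoint by time on pump, which arises only afterwards; an ITT subject without surgery has no value and no rule says what happens, while the composite baseline of SAP 5.1 is left out of the model

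*SAP*

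**What the plan says.** **Endpoint.** SAP 5.1 defines the primary endpoint as the "geometric mean of the ratios of the maximum PreOp value (Visit 1b or Day 1 PreOp) over Baseline (Visit 1a", the pre-dose visit). Footnote 8 of the Event Schedule (Protocol 5) places the last of these samples within 4 hours before surgery. The same SAP section gives a formula for a composite baseline ("Baseline for this composite endpoint is calculated as" the cube root of the product of the three baseline biomarkers).

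**Model.** SAP 7.5.1 states for the ANCOVA on the log endpoint: "The model will include treatment group as main effect, and surgery type and time on-pump as covariates". Its CMH sensitivity test uses the same two factors as strata. No baseline term is listed.

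**General rule.** SAP 7.5 is softer: "Surgery type and time on pump may be used as covariates in ANCOVA or MMRM". It also allows other variables and leaves the choice to a blinded review before any unblinded analysis. For stratification, pump time is cut at 90 and 120 minutes, the approximate tertiles "of the distribution in the MITT population".

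**Populations.** SAP 7.5 analyses the primary endpoint in both ITT and MITT. ITT (SAP 3.1) requires eligibility, dosing, and biomarkers at baseline and before surgery, but not surgery itself. MITT (SAP 3.2) requires surgery without delay and evaluation to the end of the index hospital stay. SAP 7.4.1 tabulates dosed and operated subjects separately: "study drug-treated subjects, and subjects receiving surgery will be provided overall and by treatment group".

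**Missing data.** SAP 7.2 has replacement rules for creatinine and eGFR and for biomarkers outside the quantification limits. It has none for a missing covariate.

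**The concern.** A covariate in a randomised comparison should be fixed before treatment. Time on pump comes after randomisation, after dosing and after the endpoint has been measured. It cannot be a cause of the endpoint; at most the two share patient characteristics.

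The practical consequence falls on the ITT analysis. A subject who is dosed, gives a Visit 1b or pre-operative sample and then is not operated on has a complete primary endpoint but neither a pump time nor a pump stratum. A standard ANCOVA fit and a stratified CMH test both discard such a record. The result labelled ITT would then carry an unstated post-randomisation exclusion, of unknown size and unknown balance across arms.

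The baseline term is a separate and smaller matter. The SAP adjusts the creatinine ANCOVA for baseline (7.5.3.2) but does not adjust the biomarker composite for the baseline that it has defined.

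**Working it through.** **1. The plan's own figure.** SAP 7.1 gives log scores of 1.30 (SD 0.56) for high dose, 1.07 (0.52) for low dose and 0.19 (0.19) for placebo, and states more than 80% power at 10 per group, two-sided 0.05. A two-sample t calculation with unequal SDs gives 99.97% for high dose (difference 1.11) and 99.5% for low dose (difference 0.88). The statement holds. It uses no covariates, and at the protocol's 42 per group power is practically 100% whatever the model.

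**2. Who could be lost.** Visit 1b is done only in subjects dosed 36 to 48 hours before surgery (Protocol 9.7.3). These subjects can have an endpoint well before the operation. The others have one only if surgery falls through after the pre-operative sample. Delayed-surgery subjects do have a pump time and stay in the ITT model. MITT loses nobody.

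**3. Precision cost if k of 126 are dropped.** The documents give no rate, so 2, 5 and 10% are assumed, i.e. k = 3, 6 and 13. The standard error is multiplied by √(126/(126−k)):

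| k | SE factor |
|---|---|
| 3 | 1.012 |
| 6 | 1.025 |
| 13 | 1.056 |

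**4. Shift if the loss is one-sided.** Suppose a fraction f is lost from the high-dose arm only, and those lost differ from the arm mean by d = 0.28 or 0.56 log units (0.5 or 1 SD; assumed). The arm mean moves by f·d/(1−f). The reference contrast is 1.11, a ratio of e^1.11 = 3.03.

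| f | Shift (log) | Change in ratio, either direction |
|---|---|---|
| 0.02 | 0.0057 to 0.0114 | 0.6 to 1.1% |
| 0.05 | 0.0147 to 0.0295 | 1.5 to 3.0% |
| 0.10 | 0.0311 to 0.0622 | 3.2 to 6.4% |

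**5. Cost of the pump term itself, if unrelated to the endpoint.**
- ANCOVA: added to treatment and surgery type (5 parameters), it multiplies the interval width by [t(N−6)/t(N−5)]·√(1+1/(N−6)). This is 1.004 at N = 126 and 1.010 at N = 60.
- CMH: 3 surgery types (SAP 7.5.3.5) × 3 pump classes = 9 strata. A pairwise comparison has 84/9 = 9.3 subjects per stratum at 42 per group and 40/9 = 4.4 at 20 per group. With surgery type alone the figures are 84/3 = 28 and 40/3 = 13.3.
- CMH simulation (3,000 trials, shift 0.4 SD, several assumed surgery mixes): efficiency of 9 strata relative to 3 was 0.86 to 0.90 at 42 per group and 0.75 to 0.80 at 20 per group.

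**6. Gain from the baseline covariate.** Assume equal log variance s² at baseline and follow-up in placebo, with correlation r. Then 0.19² = 2s²(1−r), the slope of the log ratio on log baseline is −(1−r), and the variance removed per arm is 0.19²(1−r)/2. Taking the same amount in the active arm, the share of the contrast variance removed is 0.19²(1−r)/(SD_active² + 0.19²). The denominators are 0.3497 (high) and 0.3065 (low).

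| Assumed r | High dose | Low dose |
|---|---|---|
| 0.8 | 2.1% | 2.4% |
| 0.7 | 3.1% | 3.5% |
| 0.5 | 5.2% | 5.9% |
| 0.3 | 7.2% | 8.2% |

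**The case against.** The strongest reply is that the harm is inferred. No sentence in the SAP drops a non-operated subject; that is what software does by default. The number may be zero, and every rate above is assumed. This stands, and it limits the size of the point. It does not remove the gap, because the SAP gives no other handling.

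A second reply is that SAP 7.5 already lets the blinded review take pump time out or add a baseline term. That route exists. But 7.5.1 commits to pump time, 7.5 does not name baseline, and neither says what happens to an ITT subject without surgery. The *may* of 7.5 and the *will* of 7.5.1 can be reconciled by reading 7.5.1 as the specific choice, so this is loose wording rather than a contradiction.

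Several stronger readings are tempting and are not supported:

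- *ITT collapses into MITT.* It does not. ITT keeps subjects whose surgery was delayed and those not followed to the end of the index stay.
- *Surgery type is lost as well.* 7.5.1 says only surgery type. The scheduled type is needed for inclusion criterion 4, so each eligible subject has one.
- *Pump time cannot predict the endpoint.* Too strong: patient severity could link the two. The costs in step 5 assume no link.
- *The adjusted estimate is biased.* In simulation at 42 per arm the low-dose estimate (true difference 0.88) moved by about ±0.03 to ±0.05, but only when drug shifted pump time by 0.25 to 0.5 SD and pump time correlated ±0.3 with response. Both are assumptions. With either absent there was no bias.
- *Omitting baseline invalidates the model.* It does not. Baseline is already the denominator of the ratio; only precision is at stake.
- *The CMH loss matters at the interim.* SAP 7.3 does not say that the CMH test is run there, and it is a sensitivity test.

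**Conclusion.** The point holds as a pre-specification weakness that should be corrected before unblinding. Time on pump is a post-dosing, post-endpoint variable in the primary ANCOVA and CMH strata. As written, it can remove valid endpoints from the ITT analysis without a stated rule.

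The size is modest and conditional. For assumed losses of 2 to 10%, the standard error rises about 1 to 6%. A one-sided loss at those rates would move the high-dose ratio by 0.6 to 6.4%, given an assumed difference of 0.5 to 1 SD in those lost. A reader might infer a threat to power or to type I error. Neither follows: power is near 100% on the SAP 7.1 inputs, and no error-rate inflation is shown. The baseline covariate is a precision gain of about 2 to 8% of contrast variance, resting on assumed placebo correlations and on the SAP 7.1 SDs recurring in surgical patients.

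**What to change.** In SAP 7.5.1, for both ITT and MITT:

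- Model the log primary endpoint on treatment, planned surgery type (the inclusion criterion 4 category) and log composite baseline as defined in 5.1. Analyse each component in the same way with its own log baseline.
- Remove time on pump from this ANCOVA, and stratify the CMH test by planned surgery type only, so that every ITT subject is analysed.
- If a pump-adjusted result is wanted, give it as a supportive MITT analysis.

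In SAP 7.5, state that this primary model is fixed and not open to the blinded-review choice.

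The change should not be accompanied by newly naming pump time as a covariate elsewhere. For the tubular injury composite (7.5.2.1) it is still a post-dosing variable. With an assumed drug shift of 0.25 to 0.5 SD, an assumed correlation of 0.3 and the SD of 0.51 from SAP 7.1, adjustment would move the estimate by 0.3 × 0.51 × 0.25 to 0.5 = 0.04 to 0.08 log, against a design difference of 0.4. The averaged sensitivity composite in 5.1 is described as the "geometric mean of the ratios of average of Day 1 PostOp through Day 3 over baseline", yet its area calculation starts at Visit 1b or Day 1, which is a pre-operative value. Pump time does not fit that average either.

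The cost is a few SAP sentences and minor programming. Baseline biomarkers are already collected. Planned surgery type must be known to check eligibility; if the eCRF has no separate field for it, it has to be taken from source. The baseline term uses one degree of freedom.

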### 7.5.2 Secondary Efficacy Endpoint Analysis

#### 7.5.2.1 Max PostOp over baseline in the composite of renal tubular injury biomarkers

The secondary endpoint (geometric mean of the ratios of maximum PostOp over baseline in renal tubular injury biomarkers, Section 5.2.1) will be summarized and analyzed similarly to the primary endpoint.

Likewise, each component of the composite endpoint

- $\frac{\text{max KIM-1 PostOp through Day 3}}{\text{Baseline KIM-1}}$
- $\frac{\text{max(CysC PostOp through Day 3)}}{\text{Baseline CysC}}$
- $\frac{\text{max(NGAL over PostOp through Day 3)}}{\text{Baseline NGAL}}$

will be analyzed similarly to the composite endpoint.

A sensitivity analysis will be conducted for the maximum of the ratios of maximum PostOp over baseline in renal tubular injury biomarkers (see Section 5.2.1).

### 7.5.2.2 Reduction in Urine Output

The proportion of subjects with reduction in urine output (ie, subjects with a documented AE of sustained reduction in urine output, oliguria, or anuria) through Day 5 will be presented for each treatment group. Reduction in urine output (yes/no) will also be analyzed using the Fisher's exact test for the comparison between each active treatment group and the placebo group.

### 7.5.2.3 Incidence of AKI

Incidence of AKI through Day 5 defined in Section 5.2.3 will be presented using proportions and analyzed using the Fisher's exact test as described above for reduction in urine output.

As a sensitivity analysis, subject incidence of  $\geq 0.3$  mg/dL and  $\geq 0.5$  mg/dL increase from baseline over 2 consecutive measurements at least 12 hours apart in serum creatinine from post-cardiac surgery through Day 5 will be analyzed similarly.

## 7.5.3 Exploratory Analysis

### 7.5.3.1 Severity of AKI

Maximum severity of AKI through Day 7 will be summarized by presenting the proportion of subjects in each severity stage in each treatment group. CMH test for the row mean score difference will be used for the between active treatment and placebo difference stratified by the surgery type and time on pump. A modified ridit score will be used in the CMH test.

### 7.5.3.2 Mean increase from baseline in serum creatinine

Mean changes and % mean changes from baseline (defined as Visit 1a) to the mean of creatinine PostOp through Day 7 (or discharge if earlier) will be summarized by treatment group. The between active treatment and placebo difference in mean change and % mean change will be analyzed using ANCOVA with treatment as main effect and baseline as a covariate. LSM difference and the associated 95% CI will be presented.

Additionally, the CMH test stratified by the baseline creatinine in approximately tertile ( $\leq 0.9$ ,  $>0.9$  to  $1.2$ ,  $>1.2$  mg/dL) will be carried out as a sensitivity analysis.

Analysis of change and % change from baseline to each post-dose visit through Day 90 (i.e., Days 1, 2, 3, 4, 5, 6, 7, 30, 60, and 90) will be analyzed using the mixed effects model for repeated measures (MMRM), which includes treatment, visit, and treatment-by-visit interaction as factors, baseline as a covariate, and subject as repeated measure unit. The LSM and 95% CI will be presented for each treatment group at each time point. In the computation, the variance-covariance matrix will be assumed AR(1) structure and the denominator degrees-of-freedom will be estimated using the improved Kenward-Rodger method. LSM and 95% for the between active dose and placebo group difference will also be presented at each time point.

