#### **7.5.3.3 Mean reduction from Baseline in estimated glomerular filtration rate (eGFR)**

Mean change and % mean change from baseline (defined as Visit 1a) in eGFR (mL/min/1.73m^2) will be summarized and analyzed similarly to that for the serum creatinine.

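### The AR(1) covariance in the exploratory creatinine and eGFR repeated-measures model forces one variance on pre-operative, acute and recovery visits, so its per-visit confidence intervals will be miscalibrated if visit variances differ

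*SAP*

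**What the plan says.** SAP 7.5.3.2 analyses change and percent change in serum creatinine at "Days 1, 2, 3, 4, 5, 6, 7, 30, 60, and 90" with a mixed model for repeated measures. The model has "treatment, visit, and treatment-by-visit interaction as factors, baseline as a covariate, and subject as repeated measure unit". For the covariance, "the variance-covariance matrix will be assumed AR(1) structure", and "the denominator degrees-of-freedom will be estimated using the improved Kenward-Rodger method". Least squares means with 95% intervals are reported for each group at each visit. For the group contrasts, "LSM and 95% for the between active dose and placebo group difference will also be presented at each time point". SAP 7.5.3.3 states that eGFR "will be summarized and analyzed similarly to that for the serum creatinine". The results go into Tables 14.2-5.2 and 14.2-6.2.

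Neither section names a heterogeneous, time-based or unstructured alternative, a robust standard error, a fallback, or a sensitivity analysis on the covariance. SAP 7.2 names SAS 9.4 or higher as the software. A request for plain AR(1) there means correlation by visit order and a single variance.

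**The concern.** AR(1) makes two assumptions that do not match this schedule. First, the variance of the change from baseline is the same at every visit. Yet the Day 1 sample is taken before surgery (SAP 6.4), one to two days after the Visit 1a baseline. Days 2-7 follow bypass surgery, after which Protocol 6.1 puts the AKI incidence at approximately 30%. Days 30-90 are recovery visits. Second, neighbouring visits have the same correlation whether they are one day or thirty days apart.

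The per-visit intervals are what this model is for. If the shared variance is wrong, intervals on the acute days, where a kidney effect would be looked for, overstate precision, and those at stable visits understate it. Kenward-Roger is a small-sample correction under the assumed structure. It does not repair a wrong structure.

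**Working it through.** The plan gives no SD, correlation or power for this model, so there is no stated figure to reproduce. The SDs and the true correlation below are assumptions.

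**What AR(1) implies.** With visits numbered j = 1 to 10, Var(Y_j) = s² for all j, and Corr(Y_j, Y_k) = rho^|j-k|. The gaps between the listed days are 1, 1, 1, 1, 1, 1, 23, 30 and 30 days. At rho = 0.7, Day 6 to 7, Day 7 to 30 and Day 60 to 90 all get 0.7.

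**Why equal variances are unlikely.** Assume that 30% of subjects have a post-operative rise of d and the rest have none. That mixture alone adds an SD of sqrt(0.3 × 0.7) × d = 0.458d. For d = 0.3 to 0.5 mg/dL this is 0.14 to 0.23 mg/dL, which the pre-operative Day 1 change lacks.

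**Large-sample approximation.** With a separate mean for each treatment and visit and complete data, coverage at a visit is about 2Φ(1.96 × SD_pooled / SD_visit) - 1. Assume an SD of 0.20 on Days 1, 30, 60 and 90, and 0.30 on Days 2-7 (1.5-fold apart):
- Pooled variance = (4 × 0.04 + 6 × 0.09)/10 = 0.07, so the pooled SD is 0.265.
- Days 2-7: 0.265/0.30 = 0.88, and coverage is 91.6%.
- Other visits: 0.265/0.20 = 1.32, and coverage is 99.0%.

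**Simulation.** Inputs were 42 per group (Protocol synopsis), the SAP's mean model, an equal-variance AR(1) fitted by REML, 400 runs, and a multiplier of 1.97 in place of Kenward-Roger. The true correlation was assumed to be 0.3 + 0.7·exp(-days/5). Coverage of the nominal 95% interval for an active-placebo difference, complete data:

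| Assumed visit SDs | Days 2-7 | Days 1, 30, 60, 90 |
|---|---|---|
| Equal (wrong spacing only) | 93-95% | 93-96% |
| 1.5-fold apart | 88-90% | 98-99% |
| 2.5-fold apart | 86-93% | 97-100% |
| 4-fold apart | 80-93% | 99-100% |

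In the 1.5-fold case the intervals were 0.84-0.85 times the width of a per-visit ANCOVA interval on Days 2-7, and 1.26-1.27 times elsewhere. A width ratio of 0.84 implies coverage of about 90% (0.84 × 1.98 = 1.66). The Monte Carlo standard error is about 1 point at 95% and 1.6 points at 89%.

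**With visit-specific variances.** Per-visit ANCOVA, a stand-in for the unstructured model with complete data, covered 93-96% at every visit in every scenario. A full unstructured model was not fitted to incomplete data.

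**With Days 4-6 partly missing through early discharge.** Equal variances gave 94-98%. In the 1.5-fold case, coverage was 90-91% on Days 2, 3 and 7, and 98-99% on Days 1, 30, 60 and 90.

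**The case against.** The strongest reply is that the analysis is exploratory, with no alpha and no decision rule attached. The protocol's creatinine objective, mean increase through Day 7, has its own ANCOVA and a stratified CMH sensitivity analysis in SAP 7.5.3.2. The visit SDs are unknown, and a two-parameter covariance is a stable choice for ten visits with some sparse days. All of this is correct. It limits the priority, but it does not make one variance plausible across surgery.

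A reader might go further and infer that the uneven visit spacing by itself makes the intervals wrong. The check does not bear this out. With equal SDs, coverage stayed at 93-96% and widths at 0.99-1.00 of per-visit ANCOVA. With complete data and a mean for each treatment and visit, the contrast at a visit depends almost entirely on that visit's variance. Contrasting AR(1) with a per-day decay, such as 0.9^23 = 0.09 between Days 7 and 30, is no evidence either. It assumes that correlation falls towards zero, which nothing in the documents supports.

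A reader might also infer that AR(1) distorts the results of subjects discharged early, since SAP Appendix A collects Days 4-6 only in those still in hospital. The documents do not settle this. SAP 7.2 fills missing creatinine and eGFR values outside the model, by local laboratory result or, before Day 7, by interpolation, and reports an early discharge value as Day 7. Whether interpolation is meant to cover planned post-discharge gaps is unclear, but these rules may leave the model little to infer.

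**Conclusion.** The concern stands in a limited form. AR(1) as written imposes a single variance on visits before surgery, just after it and in recovery. If the variances differ, which is likely, the per-visit 95% intervals for creatinine and eGFR will be too narrow where spread is large and too wide where it is small.

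The size cannot be fixed from the documents. SDs 1.5-fold apart give about 88-90% coverage on Days 2-7 and 98-99% elsewhere. Coverage near 80% appeared only with SDs 4-fold apart, and only on some acute days. All these figures rest on assumed SDs, an assumed true correlation and 42 analysed per group. It would be too strong to say that the intervals are wrong whatever the data show: with equal variances they are close to nominal.

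The primary and secondary analyses and the ANCOVA of mean change through Day 7 are unaffected. This is an inexpensive improvement to an exploratory analysis.

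**What to change.** In SAP 7.5.3.2, and by reference 7.5.3.3, replace AR(1) with an unstructured covariance and keep Kenward-Roger degrees of freedom. Pre-specify the order to follow if it does not converge, keeping visit-specific variances at each step:

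1. Heterogeneous Toeplitz (10 variances + 9 correlations = 19 parameters).
2. A simpler heterogeneous-variance structure, such as heterogeneous compound symmetry (10 + 1 = 11 parameters), with empirical sandwich standard errors. Kenward-Roger adjusts the model-based covariance, so name the degrees-of-freedom rule for this step.

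Use the first structure that converges and report which it was.

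The cost is a few sentences in the SAP and a few lines of code. The downside is more covariance parameters, 10 × 11/2 = 55 for ten visits against two for AR(1), and possible non-convergence, particularly if Days 4-6 are sparse. The fallback handles that, provided it is fixed before unblinding.
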